8.6 User Experience Survey (CHF Cohort – Post)

(5 point likert scale, 1=strongly disagree, 3=neither disagree/agree and 5=strongly agree)

Definition of application: The mobile phone application downloaded on the smart phone. It is used by participant's to respond to survey questions.

Device

1. I could use the patch anytime and anywhere throughout my daily life.
2. The patch is easy to replace.
3. The application is easy to use.

4. The patch makes me feel more secure.
5. Using the application makes me feel more secure.
6. I have doubts using the patch in the future.
7. I have doubts using this application in the future.

Home Health

8. The home health nurses are responsive to my questions and concerns.
9. My home health nurses are interested in my health.
10. The instructions given by my home health nurses are easy to follow.
11. I am satisfied with the amount of communication I receive from the home health nurses.
12. I am satisfied with the quality of my interactions with my home health nurses.

Clinical Care Team

13. The care team is responsive to my questions and concerns.
14. My care team is interested in my health.
15. The instructions given by my care team are easy to follow.
16. I am satisfied with the amount of communication I receive from the care team.
17. I am satisfied with the quality of my interactions with my care team.

Program

18. I am satisfied with the remote monitoring program.
19. The remote monitoring program allows me to stay better connected to my care team.
20. The remote monitoring program helped me eat healthier.
21. The remote monitoring program helped me take my medications on time.
22. Participating in this program makes me feel more secure in detecting problems with my health in general.
23. Participating in this program helped me stay out of hospital.
24. I would recommend this program to other patients.

8.7 Semi-Structured Interviews

Definitions

Wearable Device: Electronic devices that a person can wear, like Fitbits and smartwatches (applewatch, Samsung watch), and are designed to collect someone's personal health and exercise data, like how many steps you walked, or how fast your heart is beating.

Telemonitoring: Clinical providers using information technology, such as phone calls, video calls, chat functions, to monitor patients at a distance.

8.7.1 Pre-discharge Interview Guide (CHF)

Example of questions	Example of probing questions
What is your previous experience with using wearable devices?	
 • If no experience, probe why • Did you find it useful? How was it useful? • What were some of the challenges with it?
What is your previous experience with telemonitoring?	
 • If no experience, probe why • How did you feel about the telemonitoring? • What were some of the challenges with telemonitoring?

 • How long have you had CHF? • What happened leading up to this hospital admission? 	
 • What physical symptoms of your illness did you experience? • Who participated in the decision to go to the hospital? • What did they say? • Is this your first time being admitted to the hospital for CHF? • How do you feel about being in the hospital?

 • For CHF: How do you manage your heart condition at home? • 	
 • Is there anything you do related to diet or medications? • Tell me about some of the challenges with ... • Are your family/friends involved with managing your health? • How do you feel about ...

 • Some patients say stress makes it very hard for them to manage their CHF. Is that true for you? 	
 • Yes → When you talk about stress, what do you mean? • Can you tell me about a time when stress made it difficult to manage your CHF?

 • Some patients say feeling down or depressed makes it very hard for them to manage their CHF. Is that true for you? 	
 • Yes → When you talk about feeling down or depressed, what do you mean by that? Can you describe the feeling and how it affects you? • Can you tell me about a time when feeling down or depressed made it difficult to manage your CHF?

 • We know that managing your CHF or heart failure can be expensive. Can you give us some examples of what those expense are? Has that been a problem for you 	Can you give us some examples of how you have dealt with those expenses?
How do you feel about the upcoming discharge?	
Negative feelings – Why?
 
Positive feelings – Is being enrolled in the study part of the reason (of the positive feelings)? Why?

In what way, if any, do you think participating in this study might be beneficial to you?	
Is there anything you think we should have asked you and didn't?	

8.7.2 Study Endpoint Interview Guide (CHF)

Example of questions	Example of probing questions
Device	
Tell me about your experience using the device.	How was the patch/phone? Tell me more about that.
Home Health	Home health nurses are the nurses from Home Health that visits you at your house.
Tell me about your experience working with the monitoring nurse.	
Were there any challenges?
 
Please tell me more about that.

Do you think the monitoring nurse have good awareness of your needs?	Why or why not?
In what ways, if any, did working closely with the monitoring nurse impact your health?	Why or Why not?

Care Team	Clinical Care Team are the physicians, physician assistants, nurse practitioners and nurses who took care of you during hospitalization.
Did your cardiology team contact you, or did you contact your cardiology team during the 30 day remote monitoring period?	Yes → Complete Care team question session No → Skip entire Care team session
Tell me about your experience working with the clinical care team (for the past 30 days)	Were there any challenges? Please tell me more about that.
In what ways, if any, did working closely with the clinical team impact your health?	Why or Why not?
Program	By program, we mean the whole experience wearing the devices, interacting with home health, and clinical care team.
What was it like to be part of this program?	
How practical do you think the program is?	Were the instructions easy to follow? Were the daily requirements easy to complete? Why or why not?
What do you think about the discharge care you received for the past month? (Skip if patient is newly diagnosed during index admission)	Does it feel different than typical discharge care you received before? Why or why not? Or How does it feel different? In what ways is it different?

Do you feel like this study prevented a hospital readmission? (Skip if patient is readmitted)
	
Why or why not?

Please walk me through how you (or your caregiver) managed your HF while enrolled in the program. Has being in this program led to any changes in how you manage your heart failure?
	
What kind of changes? Tell me more about that.


Has being in this program led to any changes in how you feel about your heart failure?
	
What kind of changes? Tell me more about that. Do you feel stressed about having a HF diagnosis? Did the study help you reduce stress for the past month? Why or why not? Do you feel down or depressed about having a HF diagnosis? Did the study help you reduce depressing feelings for the past month? Why or why not?

Has the study made you feel more secure in the past month?
	
Why or why not?

Has the study empowered you to own and manage your care?
	
Why or why not? Or How/In what ways did it...

Were your family or friends assisting you with the devices?
	
How does your family/friends feel about the program? Do they feel like the program is practical? Why or why not? Does it help ease burden of care? Why or why not? Do you think you could have done the study without their assistance?

Please walk me through your feelings towards using the devices in the past month.
 
(Ex. Enthusiastic in the beginning → felt bored later or worried at the beginning → felt comfortable later)
	

I want to ask you a question for you to help us. How do you think we could make this program better?
	

Is there anything you would like to add?
	

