In addition, the monitoring nurse will double the diuretic dosing if a patient has new symptoms of shortness of breath at rest, orthopnea, postural nocturnal dyspnea, or lower extremity swelling. The double diuretic dosing will also occur if weight gain increases by ≥ 5 lbs over dry weight. If the symptom question is met, then the patient will get a 3rd question on Day n+1 that asks if the symptoms are getting better, worse or the same. If the symptoms are getting worse, the monitoring nurse will escalate to the clinical care team with a phone call. If the symptoms are getting better or are the same, the double dose of diuretic will remain unchanged. If symptoms or weight gain normalize, the double dose of diuretic will be deescalated to the standard dosing regimen.

If there is a high-risk alert, then the monitoring nurse receives an alert, which will result in a phone call to the patients and note template with patients. The monitoring nurse alert will also occur if there are a certain number of alerts (to be determined and varied during patients 1-5) and 1-4 lbs of weight gain (to be determined and varied during patients 1-5). In addition, if patients have some combination of weight gain and standard alerts or a high-risk alert, then the doubling of diuretics will also occur. If patients have a combination of 1-4 lb weight gain and a set number of device alerts, we will stop diuretic dosing if weight gain normalizes back to dry weight. The process map for patients 1-5 is shown in Figure 1. Escalating and deescalating diuretic dosing will also be built into the same note template in addition to prompts for education to ensure a standardized process from the monitoring nurses. We also have a multiple-choice option for monitoring nurse to document the care plan for participants.

[figure not shown]

Figure 1: Process map for CHF Patient 1-5

If care is escalated to the clinical care team which includes Advanced Practice Nurses, Physician Assistants and Physicians, the care team will pursue various interventions including counseling, altering medication therapy, urgent visits to heart failure clinic ideally within 72 hours, and if no other available options readmission. These workflows will be left to the discretion of the clinical care team given the nuance in taking care of these high-risk patients and the existing relationship and prior history with

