these providers. There are some standardized workflows that will be followed by the care team that are of note. If the patient has diuretic dose escalated for 3 days, then the clinical care team will make sure patient has a basic metabolic panel ordered to make sure patient's renal function is stable on the higher diuretic dose. We created a standardized note template for mid-level providers as part of the escalation pathway (Table 3). Also, all messaging from the monitoring nurse will be forwarded to the heart failure clinical pool and/or CHF APP pool per protocol to create the most rapid response back to the patient if required.

Cardiovascular symptoms not related to CHF Is the patient having any concerning cardiovascular symptoms not related to CHF? (y/n)
Pulmonary symptoms Is the patient having any concerning pulmonary symptoms not related to CHF? (y/n)
Infectious symptoms Is the patient having any symptoms concerning for an infection (eg: fever, dysuria, productive cough, diarrhea, vomiting, rash, or flu-like symptoms)? (y/n)
Urine output Does the patient have decreased urine output or are they not responding to their diuretic dose? (y/n)
Hematologic symptoms (such as bleeding and thrombosis) Is the patient having any concerning hematologic symptoms? (y/n)
Medication adherence questions 
 • In the last week has the patient missed any diuretic doses (eg: lasix, bumex, spironolactone)? (y/n/na) • In the last week has the patient missed any beta blocker doses (eg: metoprolol, carvedilol)? (y/n/na) • In the last week has the patient missed any ACE/ARB doses (eg: enalapril, lisinopril, benazepril, captopril, quinapril, irbesartan, losartan, olmesartan, valsartan)? (y/n/na)
Self-Care 
 1. Did the patient ask any questions related to self-care? (y/n) 2. Did a family member or caregiver ask any questions related to self-care? (y/n) 3. Did the patient or a family member or caregiver know their medications? (y/n) 4. What led to your communication with the patient? (monitoring nurse recommendation, patient called, abnormal lab finding, other)
Assessment 
 1. What do you think is the cause of the patient's decompensation? (HF exacerbation, cardiovascular non-HF, pulmonary, infectious, renal, other) 2. On a scale of 1 to 5 how confident are you in this choice? 1 being least confident, 5 being extremely confident (select number 1-5 from drop down menu)

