4.2 Inclusion and Exclusion Criteria

4.2.1 Patients

We will recruit CHF patients

CHF Cohort

Inclusion Criteria:

- Patient is an inpatient at Evanston Hospital
- Patient is followed by the heart failure clinical team post-discharge
- Patient has a history of heart failure
- Patient received at least one dose of IV diuretic during index hospitalization
- Patient is monitored by monitoring nurse post-discharge
- Patient discharges with any home health service
- Symptoms corresponding to NYHA function class II-IV
- Patient has heart failure with reduced left ventricular ejection fraction (LVEF)<40%, or HF with mid-ranged ejection fraction (LVEF 40-50%), or HF with preserved ejection fraction (LVEF≥50%)
- Patient is in the top 50% risk of readmission across NorthShore University HealthSystem's CAPE 30-day readmission model
- Patient is at least 18 years of age
- Patient is fluent in English
- Patient agrees to protocol-required procedures

Exclusion Criteria:

- Patient has cognitive or physical limitations that, in the opinion of the investigator, limit the patient's ability to maintain patch/wrist device, phone

- Patient has allergy to hydrocolloid adhesives
- Patient has present skin damage preventing them from wearing a study device
- Patient has renal dysfunction requiring dialysis
- Pregnancy

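### The endpoint interview guide defines the Clinical Care Team as hospital staff, while the protocol uses the term for the post-discharge heart failure team that receives escalations

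*Protocol*

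**What the plan says.** The Care Team block of Section 8.7.2 starts with a definition addressed to the patient: "Clinical Care Team are the physicians, physician assistants, nurse practitioners and nurses who took care of you during hospitalization". Three questions follow.

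- A gate question: "Did your cardiology team contact you, or did you contact your cardiology team during the 30 day remote monitoring period". A no skips the whole block.
- An experience question: "Tell me about your experience working with the clinical care team (for the past 30 days".
- An impact question: "In what ways, if any, did working closely with the clinical team impact your health".

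The Program block that comes next relies on the same term: "By program, we mean the whole experience wearing the devices, interacting with home health, and clinical care team".

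Section 2.2 gives the team a post-discharge role. The workflow text begins "If care is escalated to the clinical care team which includes Advanced Practice Nurses, Physician Assistants and Physicians" and goes on to the responses open to that team, such as counselling, medication changes and urgent clinic visits. Messages from the monitoring nurse are "forwarded to the heart failure clinical pool and/or CHF APP pool per protocol". An inclusion criterion in Section 4.2.1 reads "Patient is followed by the heart failure clinical team post-discharge".

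**The concern.** Section 3.1 sets out to evaluate, by interview and survey, how patients perceive the escalation pathways to nurses and physicians, and Section 3.2 (part II) repeats the aim. The Care Team block is the part of the endpoint interview devoted to the clinicians at the receiving end of that pathway. If the patient is told that these clinicians are the people who treated them on the ward, two things can go wrong. A contact with the clinic may not be recognised as contact with the team, and the block is skipped. Or views about inpatient care, which the study did not change, may be recorded as views about the monitoring programme. With a planned enrolment of 20 patients (Section 4.3.1), a few lost or misdirected answers would be noticeable in the thematic analysis.

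**Working it through.** No arithmetic applies. The check is a comparison of the texts.

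**Who the team is**

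- Section 8.7.2: the staff of the hospital stay, including its nurses.
- Section 2.2: the clinicians to whom care is escalated after discharge, reached through the heart failure clinical pool and/or the pool of CHF advanced practice providers. The nurses this passage names are advanced practice nurses, although the list is introduced as what the team includes and need not be complete.
- Section 4.2.1: the heart failure team that follows the patient after discharge.
- Section 9.3, the provider interview guide: the clinical team is the group that receives escalations, so patient and provider interviews attach one label to differently defined groups.

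The definition in 8.7.2 disagrees with the other three.

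**What each question fixes**

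- Gate: period stated (the monitoring period); label *cardiology team*, which is not the defined term.
- Experience: period stated (past 30 days); label *clinical care team*, the defined term.
- Impact: no period of its own, but asked only after a yes at the gate; label *clinical team*.

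So two of three questions state the period, and the third inherits it from the gate. None states which staff are meant, except through the inpatient definition.

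**What follows for different patients**

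1. No contact with either group after discharge: the block is skipped, correctly.
2. Contact with clinicians who also treated the patient in hospital: the definition and the intended team coincide, and no error arises.
3. Contact only with clinic staff not met in hospital: a patient who takes *cardiology team* in its plain sense says yes, then meets the defined term in the next question and may answer about other people. A patient who carries the definition over to the gate says no, and the block is lost.

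Only the third group is exposed. Its size cannot be derived. Under Section 2.2, phase 1 patients are on the inpatient CHF service list and already belong to the heart failure team, which suggests overlap. Section 4.2.1 does not require that this team treated the patient in hospital, and 8.7.2 itself allows for patients first diagnosed during the index admission.

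**How many patients**

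The planned enrolment of 20 caps the interviewed group at 20, whichever interview quota applies (20 per cohort in Section 3.2, 40 in Section 4.4.1).

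**The case against.** The strongest reply is that the same table already steers the answers. The gate and the main question are tied to the monitoring period, and under Section 4.4.1 the endpoint contact comes after 30 days of monitoring, so a patient would have to disregard two explicit limits to describe ward care. The gate uses a plain label, and a patient telephoned by a heart failure clinician has good reason to say yes. Section 2.2 leaves responses to the care team partly because of its existing relationship with these patients. The guide gives example questions, and Section 3.4 provides for trained interviewers with probes and follow-up questions who can redirect a patient.

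Most of this stands, and it rules out the stronger readings. A reader might infer that the care-team answers as a whole describe inpatient care; the time limits make that unlikely. A reader might also extend the error to survey items 13 to 17 in Section 8.6. Those items sit under a Clinical Care Team heading but carry no inpatient definition, so at most they lack detail.

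What the reply does not remove is the question of identity. The time limits settle when, not who. Probing cannot recover a block that was skipped, and an interviewer working from this definition has no text that points to the clinic team.

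**Conclusion.** The definition in Section 8.7.2 contradicts the protocol's own use of the term in Sections 2.2 and 4.2.1, and the changing labels add to the ambiguity. The consequence is limited: some patients whose only contact was with unfamiliar clinic staff may skip the block or answer about the wrong people. This touches three care-team questions and, through its definition, the Program block, for at most 20 interviewed patients. Readmission and the other quantitative results do not depend on it. The conclusion assumes that the definition is read to patients or used by interviewers to explain the term, as its second-person wording suggests, and that inpatient and clinic staff are not always the same people. The protocol gives no figure for the share of answers affected. It is a minor inconsistency, worth correcting because the block serves a stated aim and the correction is almost free.

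**What to change.** Replace the definition with: *the heart failure clinic physicians, physician assistants and advanced practice nurses responsible for your heart failure care since you left the hospital*. Give this group one label and use it in the gate question and both care-team questions, keeping the existing 30-day limits; the Program definition should carry the same label. Define the team by responsibility for care and not by who made contact. Otherwise the gate would ask whether the people who contacted the patient had contacted the patient. Printing the same line above items 13 to 17 in Section 8.6 would be a convenience, not a correction. The cost is a minor wording amendment to the interview guide, with no added burden on patients or staff and no change to the analysis.

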APPENDIX 2 – PROVIDER SURVEY AND INTERVIEW

9.1 Study Start point (Demographic Survey + Interview)

Demographic Survey:

1. Please tell me your position title: _____

Interview at Study Start Point

Example of questions	Example of probing questions
What experience do you have with telemonitoring?	Yes → Tell me more about that No → No probe Vague response → Probe to see if they have telemonitoring experience (Experience during COVID-19 pandemic)
When you first heard about the program, what did you think about it?	What do you think about the workflow/protocol? What do you think about the monitoring platform?
In what ways, if any, do you think the program could be beneficial to your patients?	Why or why not?
What expectations, if any, do you have about this program as this relates to your work?	

What supports do you think you will need, if any, with implementing remote monitoring?	What do you think it will take for us to continue offering this as standard of care?

For clinical team: How do you feel about implementing patient remote monitoring with Home Health?
 
For home health: How do you feel about implementing patient remote monitoring with the regular care team?
	Why or why not?
What concerns do you have about this program, if any?	
Yes → Tell me more about that
 
No → No probe
 
Vague response → Probe

Is there anything you think we should have asked you and didn't?	
For HF providers only:	
What are your experiences with taking care of cardiology patients?	
What about HF patients?
 
Can you walk me through taking care of a typical HF patient after discharge?
 
What were some challenges with patient care?
 
How do you think this study would help with patient care?

Sometimes patients have difficulty with treatment plan adherence and as a result they adapt based on their life situations.	
What do you think about this?
 
Is this frequent in HF patients?
 
What tactics do you use to assist with adherence?
 
How effective do you think they are?

What are your thoughts on the study helping with patient communication?	Do you expect the communication to be more targeted and efficient?
It has been reported in the literature that when patients' heart failure symptoms are worsening and they are anxious, they frequently view readmission to the hospital as a logical choice over remaining at home. What do you think about this?	Do you think this study could provide patient more stability? Why or why not? Do you think this study could help ease patient anxiety and provide emotional support? Why or why not?
Sometimes providers think of readmission as a logical choice. What do you think about this?	Would the study set up allow you to keep patient at home vs being readmitted? Why or why not?

